9.4.3 Operational Variable(s) Definition

To describe medical events, baseline characteristics, including date of birth, gender, date of diagnosis, and underlying condition will be extracted from medical records. Vaccination history will be extracted from immunization records.

9.4.4 Advisory Committee(s)

There is no Advisory Committee for this study.

9.5 Study Size

There is no planned number of vaccinees. The study will describe all eligible medically attended events that require emergency room visit or hospitalization in the study population.

Approximately 245,000 infants and toddlers aged 2-23 months were enrolled in the KPSC health plan in the period from 2011 to 2013. Among this population, there were around 60 children aged 2-23 months old with high risk conditions. It is estimated that the number of infants with high risk conditions would likely fall between 60-100 in the study

9.6 Data Management

9.6.1 Data Processing

Data collection and retrieval will be performed using the HMO's standard procedures in agreement with GSK. Quality assurance measures as implemented at the HMO will be used.

Blinding

This study is an open-label study conducted in a routine medical care setting. Reviewers are not blinded to the patient identity or vaccination status. All study staff with access to protected health information are trained in procedures to protect the confidentiality of subject data.

Data linkage

An important aspect of the KPSC managed care environment is its integrated approach to the delivery of medical care. This approach depends on, and therefore facilitates, the development and maintenance of a large number of databases, linkable through a unique medical record number. These databases include those that track membership, encounters, claims, pharmaceuticals dispensed and appointments. They also include test results as well as text excerpts of their interpretation. There are also a number of derivative files that have been developed for research purposes, including those for disease identification, geocoding files and mortality follow-up files.

9.6.2 Software and Hardware

The data analysis in this study will be performed by Research & Evaluation programmers and analysts in KPSC. SAS (Enterprise Guide 4.3 or higher) will be used to perform data programming and data analysis in the study. Data management will be done in both PC and Unix environments.

9.7 Data Analysis

9.7.1 Statistical Hypotheses

This study is descriptive in nature and there will be no hypothesis testing.

9.7.2 Analysis of Demographics and Baseline Characteristics

Age at vaccination (extracted from date of birth and date of vaccination) will be presented by mean, median, standard deviation, minimum and maximum. Gender will be described by absolute numbers and percentages. Vaccination history (including vaccine name and age or relative timing of vaccination) will be summarized descriptively.

9.7.3 Statistical Methods

This descriptive study will analyze collected data to report frequencies of MenACWY-CRM exposure and analysis of medical events. The frequencies will be presented as absolute numbers and percentages of relevant total.

Frequency of exposure to MenACWY-CRM vaccination

This descriptive study will report the frequency of exposure among infants and toddlers 2-23 months of age vaccinated at least one dose of MenACWY-CRM during the study period. Frequency of exposure will be summarized as follows:

- Overall
- 1 dose
- 2 doses
- 3 doses
- 4 doses

Analysis of medical events

Eligible medical events in the study will be described as follows:

- Frequency of individual medical events

The frequency of medical events is defined as the total number of each individual event. The frequency will be described by absolute number of each individual medical event and percentage of each individual medical event of total number of captured medical events during the observation period.

If the number of medical events allows, captured medical events will be stratified by dose.

- Rate of medical events

The rate of medical events is defined as the number of all captured events divided by the total person-time following MenACWY-CRM doses administered during the study period. 95% confidence interval of the rate of medical events will be calculated. Person-time for each dose will begin at the vaccination and end at 6 months following vaccination, disenrollment, death, the end of data collection, or receipt of an additional dose of MenACWY-CRM, whichever comes first. If data permit, rate will be further stratified by dose.

▫ Description of medical events

Medical events following MenACWY-CRM exposure in children 2-23 months of age will be described. Medical events will be reviewed and described, at least including age at vaccination, gender, vaccination history, diagnoses, and if available, underlying condition. Recurrence of the same medical event after repeated MenACWY-CRM vaccination of the same person will be included in the description as well.

9.7.4 Statistical Considerations

Misclassification of diagnosis

As this study focuses on medical events requiring hospitalization and emergency care among children 2-23 months of age enrolled as KPSC health plan members, it is unlikely that serious and acute outcomes would be missed or misclassified. Also, due to the ICD-9 to ICD-10 transition, both ICD-9 and ICD-10 codes may need to be searched to exclude pre-existing conditions. Some pre-existing conditions may be missed from the automated search due to imperfect mapping between ICD-9 and ICD-10.

Misclassification of exposure

Depending on the available data in the medical record database on the recording of a vaccination, it may be that not all vaccinations are given through the HMO, resulting in not all vaccination data being present in the medical record. However, loss of these data should not affect results because analyses are confined to those individuals with a recorded vaccine administration.

Missing Data

No imputation will be performed. We expect there to be a very low rate of missing data regarding population characteristics, such as age and gender, and diagnoses. The study uses electronic medical records as the source of information for diagnoses, so events that do not result in a medical visit may be missed. Subjects missing the stratification factors will be excluded from subgroup analysis where the stratification factor is unknown. We expect that most vaccines will be captured by the electronic medical record, with very little missing information. It is possible that some study subjects will have received meningococcal vaccine prior to joining the health plan, and these prior doses may not be captured. This number is expected to be small and not to have a material impact on the results.

Handling of Loss to Follow-up

We expect there to be minimal loss to follow-up due to the high retention of KPSC health plan members in this age group. Any loss will be addressed in the data analysis by the truncation of person-time in the event rate calculation.

9.8 Quality Control

9.8.1 Validation

Vaccination and medical event data will be extracted directly from the electronic medical record, which is the legal record of all medical care received within the KPSC system. Records of vaccinations and medical events can only be entered by medical staff, and are assumed to be an accurate representation of care received. No validation will be performed regarding vaccination. Medical events will be individually reviewed in order to determine the primary reason for the encounter as well as whether the condition predated the first receipt of MenACWY-CRM.

All data in the study is extracted and maintained in the electronic database at KPSC. The database is maintained on a daily basis, and undergoes quality validations regularly. Only authorized study personnel with passwords can access to databases. Validations of data in the study database will include range and consistency checks.

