Plan Prepared by: PPD, MS
Research Manager, Biostatistics
Kaiser Permanente Southern California

Version and Date: Version 2.0: 17 November 2015

Approvals

Approvers, Organization & Role	Approval Status	Date
PPD [REDACTED], MS KPSC Research and Evaluation Research Manager, Biostatistics	Approved	11/17/2015
PPD [REDACTED] KPSC Research and Evaluation Principal Investigator	Approved	11/17/2015
PPD [REDACTED] Department of Epidemiology GlaxoSmithKline Epidemiologist	Approved	11/17/2015

Publication Record

Version	Date	Primary Author	Description
1.0	September 18, 2015	PPD [REDACTED]	1 st Draft for GSK Review
1.1	October 16, 2015	PPD [REDACTED]	2 nd Draft for GSK Review
1.2	October 30, 2015	PPD [REDACTED]	Final draft for GSK Review
1.3	November 6, 2015	PPD [REDACTED] [REDACTED]	Comments on Draft 1.2
1.4	November 11, 2015	PPD [REDACTED]	Final draft for GSK Review
2.0	November 17, 2015	PPD [REDACTED]	Approvals obtained, SAP finalized

Definitions

Concomitant vaccination(s) – any other vaccination(s) administered to a subject on the same date as a MenACWY-CRM vaccination.

Day 0 - For the calculation of study day, Day 0 is the date when the index vaccination is received.

Event – Events are classified on an encounter level and a diagnosis level. For encounters, an inpatient admission, emergency department (ED) visit, or an ED visit resulting in an inpatient admission will each be treated as a single event. For diagnoses, all medical diagnoses made during ED and inpatient visits are considered events, which will be further classified as pre-existing, new, recurrent, or part of an ongoing episode.

Episode – Diagnosis-type medical events that result in multiple encounters during the observation period are considered episodes. Episodes comprise the course of a disease or condition, from initial presentation through resolution, as determined through chart review. An episode will be consolidated as a single event for analysis. For each episode, the first diagnosis date in any care setting will be used for analyses.

First-dose - no prior dose of a quadrivalent meningococcal conjugate vaccine recorded in the full medical history

Index vaccination – The first receipt of MenACWY-CRM at a KPSC facility between July 1, 2014 and June 30, 2017 in a study subject of which the date of administration defines the start of the observation period.

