2. STUDY OBJECTIVES

To describe medical events that require emergency department (ED) visit or hospitalization in 6 months following routine MenACWY-CRM vaccination in children 2-23 months of age in a health maintenance organization (HMO) in the United States.

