3. STUDY DESIGN

3.1 Overview of study design

This study is a descriptive observational study expected to span multiple years. This study will include members of Kaiser Permanente Southern California (KPSC) HMO vaccinated with MenACWY-CRM as part of their routine clinical care. Patients will be between the ages of 2 and 23 months.

The vaccination period spans three years, with the number of study subjects determined by the number of KPSC members aged 2-23 months who receive their index MenACWY-CRM vaccination between July 1, 2014 and June 30, 2017. The observation period for each recipient is defined as the time from the first dose of MenACWY-CRM vaccination up to 6 months after the last dose of MenACWY-CRM vaccination received between 2-23 months of age, disenrollment, death, or the end of data collection (November 30, 2017), whichever occurs sooner. Vaccination status is obtained from the information in the vaccination records of the electronic medical record (EMR).

Medical events in ED and inpatient care units in children 2-23 months of age who were vaccinated with any dose of MenACWY-CRM vaccine will be described. Medical events that occur up to six months following a dose of MenACWY-CRM, receipt of a subsequent MenACWY-CRM vaccination, disenrollment, death, or the end of data collection, whichever occurs sooner will be captured. Events will be identified from EMRs of ED and inpatient care encounters. Events with a history of the same diagnosis prior to the first dose of MenACWY-CRM vaccination will be excluded as a pre-existing condition. Medical records of these events will be reviewed and described.

All events occurring during the observation period are assessed retrospectively. One subject can experience multiple different events. All identified events will be reviewed by a general physician (study co-investigator) to determine the final diagnosis/diagnoses for the encounter.

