5.1 Identification and review of events

Medical events occurring in ED and inpatient settings within 6 months following a MenACWY-CRM vaccination will be searched in the EMR.

Medical events will be characterized two ways: by encounter (hospitalization only, ED only, or both ED and hospitalization) and by diagnosis (see Appendix A, Table Shell 4 for details). The analysis allows for any recurrent events (i.e. different episodes of the same diagnosis) to be counted independently.

For characterization by encounter (Table 4a), all dates used for analysis will be the date of the ED encounter or hospital admission. Encounters will be considered pre-existing if all diagnoses made during the encounter are present in the medical record prior to the first dose of vaccine. Upon chart review by the study physician co-investigator, an encounter will be refuted if it is found to not be a true ED or hospital encounter. Each encounter will be reported as a single event, regardless of the number of diagnoses made during the encounter.

For characterization by diagnosis (Table 4b), all dates used for analysis will be the first date that the diagnosis is recorded in the EMR in any medical setting. A diagnosis will be excluded as pre-existing if the same ICD diagnosis code appears in any medical setting prior to the first dose of MenACWY-CRM vaccination. A diagnosis will be considered refuted if, upon chart review by the study physician co-investigator, there is no evidence of the diagnosis in the medical record. Multiple diagnoses associated with the same episode will be identified, but only the first diagnosis date (in any setting) will be counted in the analysis of each episode. Subsequent diagnoses for the same episode will be marked in Table 4b as “Diagnosis is continuation of an ongoing episode.” An episode will be considered as ended when there is symptom resolution as determined by chart review (e.g., symptoms stated to have resolved or the diagnosis/symptoms have been absent from the medical record before they are mentioned again). In the case of recurrent events, the date used will be the date of the first diagnosis in the medical record following resolution of the prior episode. Recurrent events will be marked in Table 4b as “Diagnosis is a recurrence”. Each diagnosis will be described independently. It is possible that different diagnoses from the same inpatient or ED encounter could have different diagnosis

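### Chart review must determine the primary reason for each encounter, but SAP v2.0 gives it no place, so the tables cannot separate diagnoses that led to ED or hospital care from incidental ones

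*Protocol*

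**What the plan says.** Protocol 9.8.1 (Validation) gives chart review two tasks. The first is: "Medical events will be individually reviewed in order to determine the primary reason for the encounter". The second is to establish whether the condition was present before the first MenACWY-CRM dose.

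The objective in SAP v2.0 section 2, matching Protocol 8.0, is "To describe medical events that require emergency department (ED) visit or hospitalization" in the six months after vaccination.

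SAP v2.0 then sets these rules:

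- **Definitions (Event).** At diagnosis level, "all medical diagnoses made during ED and inpatient visits are considered events".
- **Section 3.1.** The physician reviews identified events "to determine the final diagnosis/diagnoses for the encounter". A primary reason is not mentioned.
- **Section 5.1, diagnoses.** A diagnosis is refuted only if "there is no evidence of the diagnosis in the medical record". Also, "Each diagnosis will be described independently".
- **Section 5.1, encounters.** Each encounter is one event however many diagnoses it carries. It is treated as pre-existing only when all of its diagnoses were on record before the first dose.
- **Section 5.4.** No sensitivity analyses are planned.

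**The concern.** The objective turns on the word require. A child may come to the ED for one problem and leave with several diagnoses recorded, only one of which explains the visit. The protocol asks the chart reviewer for the fact that tells these apart, and the SAP then makes no use of it.

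Three things are at stake. A reader of Table 5b or 6 will take each row as a condition that needed ED or hospital care, and Protocol 9.9 encourages this by saying that the described events will be severe because of the care setting. That does not follow for a secondary diagnosis. Table 5a, the other view, has rows by care setting only. And with 60 to 100 high-risk children expected (SAP 3.2), a few visits with many codes can shape the tables without any planned output showing it.

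**Working it through.** **1. Trace of the two review tasks.** The SAP carries the second task forward as column f of Tables 4a and 4b (confirmed, but dated before index). The first appears in no section or shell:

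| Output | Unit counted | Use of primary reason |
|---|---|---|
| Tables 4a, 5a | encounter, by setting | none |
| Tables 4b, 5b | diagnosis or grouping | none |
| Table 6 | diagnosis or grouping with at least 5 episodes | none |

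**2. Diagnosis count.** Table 4b gives i = a − b − e − f − g, where a = identified, b = pre-existing, e = refuted, f = before index, g = continuation of an episode. For a diagnosis that is real and new but was not why the child came: a = 1 and b = e = f = g = 0, so i = 1. It enters Table 5b and counts towards the five episodes for Table 6. It may even have been first made in clinic after vaccination, since dating uses the first record in any setting while capture needs only its appearance at an ED or inpatient visit.

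**3. Encounter count.** Table 4a gives g = a − b − e − f. Take a visit whose main reason is pre-existing but which carries one new incidental code. Not all diagnoses are pre-existing, so b = 0. The visit was real, so e = 0. Column f does not say which diagnosis decides when there are several; read in line with section 5.1, f = 0. Then g = 1 and the visit is kept.

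**4. Size.** The plan states no figure on this point, and gives no number of diagnoses per encounter. An illustration shows only where the number would matter.

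- From SAP 3.2: 60 children (low end of the expected range), one person-year each, and 10 encounters per 100 person-years (one of its tabulated rates). So E = 60 × 10/100 = 6 encounters, or 100 per 1000 person-years.
- Assumption, not in the documents: each encounter yields m new, confirmed, non-continuing diagnoses, one of them the primary reason.
- Pooled diagnoses = m × E; non-primary share = 1 − 1/m.
- Exact Poisson limits, which reproduce all twelve intervals in the SAP 3.2 table to within 0.1 (for example 74.2–131.8 at rate 100, N=50).

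| m | Pooled diagnoses | Rate per 1000 person-years (95% CI) | Non-primary share |
|---|---|---|---|
| 1 | 6 | 100 (37–218) | 0% |
| 2 | 12 | 200 (103–349) | 50% |
| 3 | 18 | 300 (178–474) | 67% |
| 4 | 24 | 400 (256–595) | 75% |

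Where these rows would apply:

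- **A single-diagnosis row of Table 5b:** they do not. A visit adds at most one event to each row. The effect there is that incidental cases of that diagnosis join the cases that led to a visit.
- **A grouping that pools several codes from one visit:** they can. With exactly m codes per visit, the pooled count has variance m²E against the Poisson mE, so the standard error is understated by √m (1.41, 1.73 and 2.0 for m = 2, 3 and 4).
- **The percentage columns:** SAP 5.2 divides by all included events. A condition that was the reason for 3 of 6 visits, and recorded at no other, is 3/6 = 50% of reasons but 3/12 = 25% of diagnoses at m = 2.

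**The case against.** The strongest reply is that counting all diagnoses is what the protocol intends. The sentence in 9.8.1 sits under quality control and is not a counting rule. Protocol 9.4.2 makes an event eligible if it falls in the observation period and is not pre-existing, and it collects the diagnosis codes from each visit. Protocol 9.7.3 bases the rate on all captured events and describes diagnoses in the plural. In descriptive surveillance with no comparator, an inclusive count is defensible, and ranking it second could play down a new condition found during an admission for something else. Tables 4a and 5a already count each visit once.

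Most of this stands, and it rules out three stronger readings that a reader might infer:

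- **That the protocol defines one event per encounter, classified by primary reason.** It does not. It orders the reason to be determined and is silent on its use.
- **That every coded diagnosis counts.** Pre-existing, refuted, pre-index and continuing diagnoses are removed. A chronic condition coded in any setting before the first dose is largely dealt with, apart from the imperfect ICD-9 to ICD-10 mapping that the SAP admits.
- **That the rates in Table 5b are inflated two- to four-fold.** The shell has no all-diagnosis total row, its single-diagnosis rows are not multiplied, and the factors are assumed.

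The SAP leaves its dataset contents to a separate data dictionary, so the reason might be recorded there. Even so, no listed table would report it. The reply does not explain why a required review result goes unused when the objective depends on it.

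**Conclusion.** The gap between protocol and SAP is real. The protocol text dated 11 August 2016 contains the requirement, and SAP v2.0 of 17 November 2015 has no place for it. As planned, the tables show how many encounters occurred and which new diagnoses were recorded at them, but not which diagnoses brought the child to ED or hospital care. Encounters with a pre-existing main reason can also remain in the count.

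The direction is clear: non-primary diagnoses can only add to the diagnosis counts, and the all-diagnoses rule can only keep more encounters in. The size is unknown. It depends on how many new, confirmed diagnoses a visit yields, and on how diagnoses are grouped, which the SAP leaves open. The conclusion rests on reading column f of Table 4a in line with section 5.1. It does not make the all-diagnosis analysis wrong. This is a cheap improvement that lets the study answer its own question.

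**What to change.** 1. Have the study physician, who already reviews all identified events, mark the primary reason for each encounter, and state this task in SAP 3.1 and 5.1.
2. Add to Tables 5b and 6 a column for diagnoses that were the primary reason, beside the all-diagnosis counts.
3. Under Table 5a, list or group encounters by primary reason where numbers allow (n ≥ 5, the SAP's own threshold). Show there the encounters whose primary reason was pre-existing.
4. Keep the all-diagnosis analysis as planned, without making it secondary.

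The cost is one field on the review form, one column in each of two shells, and a simple grouping scheme for Table 5a. No extra reviewer is needed. The downsides are discretion in visits with several problems, for which a short written rule helps, and some sparse cells given the expected 60 to 100 children.
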